9.1 Hypothesis and Sample Size

This Phase 2 study will use Predictive Probability Designs ([Lee-2008](#)) for initial Cohorts 1 and 2. The design, hypothesis and sample size considerations for the initial Cohorts 1 and 2 are described below. Refer to [Appendix 5](#), [Appendix 6](#), [Appendix 8](#) and [Appendix 9](#) for study design and statistical considerations applicable to all contingent Cohorts 3 through 10. In summary, Cohorts 3 and 4 will also use Predictive Probability Designs with the same assumptions as the initial cohorts ([Appendix 5](#)), Cohorts 5 and 6 will use Predictive Probability Designs with revised assumptions ([Appendix 6](#)), Cohorts 7 and 8

will use confidence interval method with the revised assumptions (Appendix 8), the lead-in dose escalation portion of Cohort 9 will use the mTPI-2 design (Guo-2017; Appendix 9), and the dose expansion portion of Cohort 9 and Cohort 10 will use Simon 2-stage optimal designs (Simon-1989; Appendix 9).

In creating the statistical designs for initial Cohorts 1 and 2, the Type 1 error (α) is constrained to <0.05 and Power ($1-\beta$) is constrained to ≥ 0.90 .

ORR in accordance with RECIST v1.1 is the primary endpoint. The ORR using nivolumab in the population of advanced/metastatic urothelial carcinoma who experienced disease progression on or after treatment with a checkpoint inhibitor is assumed to be 5% (p_0); thus this rate is considered uninteresting. The target ORR using sitravatinib in combination with nivolumab in this study population is 30% (p_1). Stage 1 of enrollment will include a minimum of 9 evaluable patients in each cohort. Patients included in the evaluable population will have at least one on-study disease assessment prior to discontinuation; patients who discontinue treatment due to adverse events or withdrawal of consent prior to the first on-study disease assessment will not be included in the evaluable population. With exactly 9 evaluable patients at Stage 1, if at least 1 patient has an Objective Response, 8 additional evaluable patients will be enrolled in the treatment cohort, for a total sample size of 17 evaluable patients. If at least 3 Objective Responses are observed in a treatment cohort, further investigation may be warranted. If the true ORR is 5% (null hypothesis), the probability of early termination during the study is 0.63; the Type 1 error is equal to 0.0466 and the power is equal to 0.9045.

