Enrollment Criteria – See main protocol (inclusion and exclusion criteria changes specific to Cohorts 7 and 8 under [Appendix 8](#) are noted as such in Section 4.1 and Section 4.2).

Study Assessments and Procedures – See main protocol.

Statistical Design – Changes to statistical design, hypothesis and sample size.

Hypothesis and Sample Size

The ORR using taxanes in the population of advanced/metastatic urothelial carcinoma who have previously received treatment with a checkpoint inhibitor therapy and ADC is assumed to be 10%; thus, this rate is considered uninteresting. The design for Cohort 7 and Cohort 8 will utilize a 95% confidence interval to exclude an ORR of 10%. Assuming sitravatinib in combination with nivolumab treatment will result in an ORR of at least 25% in this treatment setting, a sample size of approximately 55 evaluable patients would be sufficient for the lower bound of a 2-sided 95% confidence interval (Clopper-Pearson method) to exclude an ORR of 10%.

The design will include a non-binding stopping rule for futility derived using East[®] software v6.5 to control the Type 2 error rate of 0.117. The Type 2 error spending function is based on the Rho family with parameter 2.0. The futility analysis will be conducted when approximately 17 evaluable patients (approximately 30% of the total number of patients) are available for the response assessment. The futility bound will be 1 or fewer observed responses among the first 17 patients.

APPENDIX 9. CONTINGENT STUDY COHORTS EVALUATING SITRAVATINIB COMBINATION WITH A CHECKPOINT INHIBITOR AND AN ANTIBODY-DRUG CONJUGATE

In the event that results in the initial study cohorts are of high interest for efficacy, one or more cohorts in patients for treatment with sitravatinib in combination with pembrolizumab and enfortumab may be added to the study. Decisions for implementation of additional cohorts in the study will be made in collaboration with the Investigators and documented for Regulators and Institutional Review Boards by an Administrative Letter to Investigators.

Based on the evolving treatment landscape of urothelial carcinoma in particular with the clinical activity of ADCs, and early efficacy and safety results from active study cohorts, and in consult with Investigators, Cohort 9 described in this appendix is considered implemented of this protocol Version 4.0. Cohort 10 also described in this appendix is pending implementation.

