7.1.5 Hypothesis and Sample Size Considerations

This Phase 2 study will use Predictive Probability Designs (Lee-2008) for initial cohort 1 and 2. In summary, Cohorts 3 and 4 will also use Predictive Probability Designs with the same assumptions as the initial cohorts (Section 6.1), Cohorts 5 and 6 will use Predictive Probability Designs with revised assumptions, Cohorts 7 and 8 will use confidence interval method with the revised assumptions, the lead-in dose escalation portion of Cohort 9 will use the mTPI-2 design (Guo-2017; Appendix 2).

In creating the statistical designs, the Type 1 error (α) is constrained to <0.05 and Power ($1-\beta$) is constrained to ≥ 0.90 .

7.1.5.1 Cohort 1 and 2:

ORR in accordance with RECIST v1.1 is the primary endpoint. The ORR using nivolumab in the population of advanced/metastatic urothelial carcinoma who experienced disease progression on or after treatment with a checkpoint inhibitor is assumed to be 5% (p_0); thus, this rate is considered uninteresting. The target ORR using sitravatinib in combination with nivolumab in this study population is 30% (p_1). Stage 1 of enrollment will include a minimum of 9 evaluable patients in each cohort. Patients included in the evaluable population will have at least one on-study disease assessment prior to discontinuation; patients who discontinue treatment due to adverse events or withdrawal of consent prior to the first on-study disease assessment will not be included in the evaluable population. With exactly 9 evaluable patients at Stage 1, if at least 1 patient has an Objective Response, 8 additional evaluable patients will be enrolled in the treatment cohort, for a total sample size of 17 evaluable patients. If at least 3 Objective Responses are observed in a treatment cohort, further investigation may be warranted. If the true ORR is 5% (null hypothesis), the probability of early termination during the study is 0.63; the Type 1 error is equal to 0.0466 and the power is equal to 0.9045.

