In the event that results in the initial study cohorts are of high interest for efficacy, one or more cohorts in patients with documented disease progression on or after a PD-(L)1 checkpoint inhibitor therapy and an antibody-drug conjugate (ADC; e.g. enfortumab vedotin, sacituzumab govitecan), in any order or in combination together. Decisions for implementation of additional cohorts in the study will be made in collaboration with the Investigators and documented for Regulators and Institutional Review Boards by an Administrative Letter to Investigators.

Based on the evolving treatment landscape of urothelial carcinoma in particular with the clinical activity of ADCs, and early efficacy and safety results from active study cohorts, and in consult with Investigators, both Cohort 7 and Cohort 8 described in this section were implemented by an Administrative Letter dated September 2019.

The ORR using taxanes in the population of advanced/metastatic urothelial carcinoma who have previously received treatment with a checkpoint inhibitor therapy and ADC is assumed to be 10%; thus, this rate is considered uninteresting. The design for Cohort 7 and Cohort 8 will utilize a 95% confidence interval to exclude an ORR of 10%. Assuming sitravatinib in combination with nivolumab treatment will result in an ORR of at least 25% in this treatment setting, a sample size of approximately 55 evaluable patients would be sufficient for the lower bound of a 2-sided 95% confidence interval (Clopper-Pearson method) to exclude an ORR of 10%.

The design will include a non-binding stopping rule for futility derived using East[®] software v6.5 to control the Type 2 error rate of 0.117. The Type 2 error spending function is based on the Rho family with parameter 2.0. The futility analysis will be conducted when approximately 17 evaluable patients (approximately 30% of the total number of patients) are available for the response assessment. The futility bound will be 1 or fewer observed responses among the first 17 patients.

7.1.5.5 Cohort 9:

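### Cohorts 7 and 8: the stated Type 2 error of 0.117 matches a normal approximation; under the plan's own Clopper-Pearson rule with 55 patients the exact value is 0.155 to 0.179

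*SAP*

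**What the plan says.** SAP 7.1.5.4 and the Hypothesis and Sample Size part of Protocol Appendix 8 describe the same design for Cohorts 7 and 8:

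- The reference ORR "is assumed to be 10%; thus, this rate is considered uninteresting".
- The combination is assumed to give a result that "will result in an ORR of at least 25% in this treatment setting".
- On size and success rule, "approximately 55 evaluable patients would be sufficient for the lower bound of a 2-sided 95% confidence interval (Clopper-Pearson method") to exclude 10%.
- "The design will include a non-binding stopping rule for futility", derived in East v6.5 "to control the Type 2 error rate of 0.117", with Rho-family Type 2 error spending (parameter 2.0) and one look at about 17 evaluable patients.
- "The futility bound will be 1 or fewer observed responses among the first 17 patients".

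Neither document gives the number of responses needed for success, says whether 0.117 is exact or asymptotic, or gives the probability of stopping at the interim look.

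On power in general, SAP 7.1.5 first lists the design types for Cohorts 1 to 9. Its next sentence begins "In creating the statistical designs, the Type 1 error" and sets Type 1 error below 0.05 and power at 0.90 or more. The matching sentence in Protocol 9.1 begins "In creating the statistical designs for initial Cohorts 1 and 2".

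**The concern.** The only success criterion for these cohorts is an exact interval, so a reader will take the Type 2 error printed with it as the error of that criterion. The error rates quoted for the other two-stage efficacy designs are exact binomial values, which strengthens that reading. If 0.117 is not the exact value, the plan understates the chance of discarding a regimen that truly has a 25% ORR. These are the largest planned efficacy cohorts (55 evaluable each), and a near miss such as 10/55 would be interpreted against the wrong false-negative risk. Whoever decides whether to follow the non-binding futility rule also lacks the power cost of doing so.

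A related inconsistency is in the SAP alone. Read as written, its general sentence claims power of at least 0.90 for designs that include Cohorts 7 and 8, although 0.117 already implies only 0.883.

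**Working it through.** **Inputs** (SAP 7.1.5.4, Protocol Appendix 8): p0 = 0.10, p1 = 0.25, n = 55, two-sided 95% Clopper-Pearson, interim look at 17, stop at 1 or fewer responses, Rho(2) spending, stated Type 2 error 0.117.

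**1. Reproducing 0.117.** Use a one-sample z-test with the critical value on the null variance and the distribution under the alternative variance, one-sided 0.025.

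- No futility look: Φ[(1.96·√0.09 − 0.15·√55)/√0.1875] = Φ(−1.21) = 0.1129.
- With a non-binding Rho(2) look at 17/55: 0.1172.
- Working backwards from 0.117: fixed n = [(1.96·0.300 + 1.190·0.433)/0.15]² = 54.1. Multiplying by the group-sequential inflation of 1.014 gives 54.9, i.e. 55.
- Interim bound Z = −0.52, i.e. 17·(0.10 − 0.52·√(0.09/17)) = 1.06 responses, which rounds to the stated bound of 1.

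One approximation therefore returns 0.117, 55 and the bound of 1 in 17 together. Other approximations at n = 55 do not: alternative variance 0.271, continuity-corrected 0.146, arcsine 0.151.

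**2. Success cut-off under the stated rule.** The Clopper-Pearson lower limit is 9.08% for 10/55 and 10.43% for 11/55. Success needs at least 11 responses.

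**3. Exact error rates at n = 55.**

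- Type 1 error: P(X ≥ 11 | 55, 0.10) = 0.0189.
- Type 2 error, futility rule overruled: P(X ≤ 10 | 55, 0.25) = 0.1554, power 84.5%.
- Type 2 error, futility rule followed: 1 − Σ P(X₁ = x)·P(X₂ ≥ 11 − x) over x = 2,…,17, with X₁ ~ Bin(17, 0.25) and X₂ ~ Bin(38, 0.25), gives 0.1787, power 82.1%.
- Ratios to 0.117: 0.1554/0.117 = 1.33 and 0.1787/0.117 = 1.53.
- Power shortfall against 88.3%: 3.8 and 6.2 points.

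**4. Cost of the futility rule.** P(X₁ ≤ 1 | 17, 0.25) = 0.0501. The nominal Rho(2) spend is 0.117·(17/55)² = 0.0112. The net power cost of following the rule is 0.1787 − 0.1554 = 0.0233.

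**5. Does "approximately 55" explain it?** Exact Type 2 error at ORR 25%, with the look kept at 17:

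| n | Cut-off | Overruled | Followed |
|---|---|---|---|
| 50 | 10 | 0.164 | 0.185 |
| 53 | 11 | 0.193 | 0.213 |
| 54 | 11 | 0.174 | 0.195 |
| 55 | 11 | 0.155 | 0.179 |
| 56 | 11 | 0.139 | 0.164 |
| 57 | 11 | 0.1235 | 0.1505 |
| 58 | 12 | 0.183 | 0.204 |
| 60 | 12 | 0.148 | 0.173 |

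No n from 50 to 60 reaches 0.117; n = 57 is the best case. The first n at or below 0.117 with the rule overruled is 63 (0.105).

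**6. Sensitivity to the assumed ORR, n = 55 (overruled / followed).** 25%: 0.155 / 0.179. 26%: 0.119 / 0.141. 27%: 0.090 / 0.110.

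**7. The other cohorts.** Exact two-stage binomial sums return the stated values: Cohorts 1 and 2 give Type 1 error 0.0466 and power 0.9045; Cohorts 5 and 6 give 0.0483 and 0.9001; the Cohort 9 expansion gives 0.048 and 90.0%; Cohort 10 gives 0.050 and 85%.

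**The case against.** The strongest reply is that 0.117 is an input to the spending function. The sentence ties it to the futility rule derived in East, while the Clopper-Pearson sentence stands in a separate paragraph and claims no power. On that reading the figure is an unlabelled design value, and 88.3% power is the reader's own inference. The documents do not give East's variance settings, so the normal-approximation origin is also inferred.

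The exact figures are conditional as well. They hold for exactly 55 patients and a look at exactly 17; a look at 16 or 18 changes the followed value to 0.187 or 0.172. Protocol 9.3.1 places the primary analysis and this futility look in the full analysis population, while the sample size counts evaluable patients. At an ORR of 26% the overruled value almost equals the stated one. The final result will be reported with an exact interval that does not depend on planning power.

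Much of this stands as qualification. The provenance should be called inferred, and the exact figures should carry their n and look size. It does not remove the mismatch, which is there whatever method produced 0.117. A Type 2 error stated for a design with a single success rule will be read as belonging to that rule, and 25% is the plan's own planning value.

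On the 0.90 sentence, one can say that it cannot have been meant for every cohort, since the Cohort 9 lead-in has no power. That supports restoring the qualifier.

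**Conclusion.** The concern holds. Under the stated criterion, with 55 patients and an ORR of 25%, the exact Type 2 error is 0.155 with the futility rule overruled and 0.179 with it followed, against 0.117 stated. Power is 3.8 to 6.2 points below the implied 88.3%. The size of the gap rests on exactly 55 patients, a look at exactly 17 and an ORR of exactly 25%; it nearly closes at 26% if the rule is overruled. That 0.117 is asymptotic is an inference, though a strong one.

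The success criterion remains valid and conservative on Type 1 error. The sample size, the bound of 1 in 17 and the Rho(2) statement are not in question, because the bound does follow from Rho(2) by normal approximation. What is wrong is the stated error rate, together with the missing cut-off and the missing cost of the futility rule.

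**What to change.** In SAP 7.1.5.4 and Protocol Appendix 8:

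1. State success as at least 11 responses among 55, with the cut-off recomputed for the number actually evaluable (11 for n = 51 to 57, 12 for n = 58 to 64).
2. Replace 0.117 with the exact values (0.155, power 84.5%, if the futility rule is overruled; 0.179, power 82.1%, if it is followed), or label 0.117 as asymptotic and print the exact values beside it. Say that they apply to n = 55, a look at 17 and an ORR of 25%.
3. Report that the bound of 1 in 17 has an exact 5.0% chance of stopping at an ORR of 25%, against a nominal spend of 1.1%, and costs 2.3 points of power. Keep the bound and the Rho(2) statement.

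In SAP 7.1.5, limit the 0.90 power sentence so that it does not cover Cohorts 7 and 8, for example by restoring the qualifier in Protocol 9.1.

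The cost is wording in two documents and a less favourable stated power. No patient number, stopping rule or success criterion changes. SAP 5.0 already provides for an amended SAP before database lock, so the SAP changes can go there.

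### The Cohort 7/8 futility bound of 1 or fewer of 17 does not deliver the stated Type 2 error spending or the stated total of 0.117 on the exact scale

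*SAP*

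**What the plan says.** SAP 7.1.5.4 (Cohort 7 and 8) and Protocol Appendix 8 (Hypothesis and Sample Size) carry the same text. The uninteresting ORR is 10%. The planning assumption is: "Assuming sitravatinib in combination with nivolumab treatment will result in an ORR of at least 25% in this treatment setting". On that basis, "a sample size of approximately 55 evaluable patients would be sufficient" for the final criterion, which is that the lower limit of a two-sided 95% Clopper-Pearson interval lies above 10%.

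The futility rule is labelled non-binding. It is described as derived with East "software v6.5 to control the Type 2 error rate of 0.117". On the spending: "The Type 2 error spending function is based on the Rho family with parameter 2.0". The look takes place "when approximately 17 evaluable patients (approximately 30% of the total number of patients) are available for the response assessment". On the threshold: "The futility bound will be 1 or fewer observed responses among the first 17 patients".

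Neither document says whether the boundary was computed exactly or by normal approximation, or which variance turned a Z boundary into a response count. Neither gives the probability of meeting the bound at any ORR.

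**The concern.** A Rho function with parameter 2 spends little Type 2 error early. At 31% of the information it releases under 10% of the total, so a reader would expect an active regimen to meet the bound about 1% of the time. A bound of 1 or fewer of 17 looks too high for that when the true ORR is 25%.

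What is at stake is the description of risk. The bound informs whether a post-ADC cohort stops at 17 patients, and Protocol 9.8 plans no Data Monitoring Committee. Those taking the decision would rely on a spending statement and a Type 2 error figure that the rule may not meet. The exact scale is the natural yardstick, because the final criterion is an exact interval. The trial's other staged designs also quote exact early-termination probabilities; for Cohorts 1 and 2, 0.95^9 = 0.63, as stated.

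**Working it through.** **Inputs** (SAP 7.1.5.4, identical in Protocol Appendix 8): p0 = 0.10; p1 = 0.25; N = 55; upper-tail alpha 0.025 (from the two-sided 95% interval); beta = 0.117; Rho parameter 2; look at n = 17, so t = 17/55 = 0.309; stop at 1 or fewer.

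**1. The plan's 0.117.** Use a normal approximation, with the null variance in the critical value and the variance at 25% for power.
- Critical proportion: 0.10 + 1.96 x 0.30/√55 = 0.1793.
- Type 2 error with no look: Φ((0.1793 − 0.25)/(0.433/√55)) = 0.113.
- Adding a look that spends exactly the Rho(2) amount gives 0.1172. The stated 0.117 is reproduced.

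**2. The plan's bound.** Solve a two-look boundary for alpha 0.025, beta 0.117 and non-binding Rho(2) futility.
- Drift 3.172; Φ⁻¹(0.0112) = −2.284.
- Interim Z bound: 3.172 x √0.309 − 2.284 = −0.52.
- Null variance: 17 x 0.10 − 0.52 x 0.30 x √17 = 1.06 responses, that is, 1 or fewer. The stated bound is reproduced.

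Other conventions, in responses of 17:

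| Convention | Cut-off | Integer bound |
|---|---|---|
| Null variance, drift from 55 patients | 1.42 | 1 |
| Arcsine | 1.01 | 1 |
| Logit | 1.44 | 1 |
| Variance at 25%, solved drift | 0.77 | 0 |
| Variance at 25%, drift from 55 patients | 0.17 | 0 |

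Steps 1 and 2 use different interim variances. The 0.1172 corresponds to the 0.17 cut-off; with a cut-off of 1.06, the step 1 model gives 0.131. The two reproductions therefore show that the figures are compatible with normal approximations, but they do not identify the setting used.

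**3. Spending at the look, exact.**
- Rho(2) allowance: 0.117 x (17/55)^2 = 0.0112 (0.0105 at t = 0.30).
- P(X ≤ 1 | 17, 0.25) = 0.0501; 0.0501/0.0112 = 4.5.
- P(X = 0 | 17, 0.25) = 0.0075. At 17 patients, 0 is the only integer bound within the allowance.
- Sensitivity to the approximate look size: P(X ≤ 1) is 0.063 at 16 patients and 0.039 at 18, against allowances of 0.0099 and 0.0125.
- At ORR 10%: P(X ≤ 1 | 17) = 0.482 and P(X = 0 | 17) = 0.167.

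**4. Total Type 2 error, exact.** The Clopper-Pearson lower limit is 9.1% with 10 of 55 and 10.4% with 11 of 55, so success needs 11 or more. With bound k always followed, Type 2 error = 1 − Σ over x > k of P(X₁ = x) P(X₂ ≥ 11 − x), where X₁ ~ Bin(17, 0.25) and X₂ ~ Bin(38, 0.25).

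| Futility rule | Exact Type 2 error |
|---|---|
| No look | 0.155 |
| 0 of 17 | 0.158 |
| 1 or fewer of 17 (stated) | 0.179 |

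The upper-tail Type 1 error of 11 or more of 55 at ORR 10%, ignoring the look, is 0.0189.

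**The case against.** The strongest answer is that the bound is probably a faithful result of the stated inputs. A standard normal-approximation boundary with Rho(2) and beta 0.117 gives 1.06 responses with the null variance, and the 0.117 itself reproduces on an approximation. On this view, an approximate boundary is being marked against an exact scale.

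That stands against one tempting inference: that the bound and the Rho(2) sentence contradict each other, so that one must be an error. The documents do not support it. They leave method and variance open, and several usual conventions lead to 1 or fewer. Deleting the Rho(2) sentence could remove a true account of the derivation.

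Three further limits on the harm also stand.
- The rule is non-binding, so meeting the bound does not oblige anyone to stop, and the Type 1 error is not inflated.
- The 0.050 is not all lost power. Always following the bound raises exact Type 2 error from 0.155 to 0.179, about 2.3 percentage points. The other 2.7 points or so (0.0501 − 0.0233) are paths that would have failed at 55 patients anyway.
- Stopping 48.2% of the time at ORR 10%, against 16.7% with 0 of 17, is what a futility look is for and is not a defect.

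The objection does not rescue the stated error control. The final test is exact, the approximation is poor at 17 patients, and neither document tells the reader that an approximation was used. The non-binding label protects Type 1 error but does not make the implied stopping risk of about 1% accurate.

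**Conclusion.** The concern holds in this form: the stated bound does not have the stated spending property, and the stated Type 2 error is not achieved. At ORR 25%, each cohort has a 5.0% chance of meeting the bound, against 1.1% implied. Across Cohorts 7 and 8, if independent and both at 25%, the chance that at least one meets it is 1 − (1 − 0.0501)^2 = 9.8%, against 2.2% at the allowance.

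Exact total Type 2 error is 0.179 if the rule is always followed, not 0.117. A reader might put the whole gap of 0.062 down to the futility look. That is not so: 0.038 (0.155 − 0.117) is there with no look and reflects the exact final criterion, and 0.023 comes from the bound.

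The result assumes exactly 17 and 55 evaluable patients, independent binomial responses, and success at 11 or more. A look at 16 or 18 patients does not bring the bound within its allowance. That the software used a normal approximation with the null variance is an inference for the sponsor to confirm; the exact figures do not depend on it. The point deserves correction but does not affect the validity of the final test.

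**What to change.** In SAP 7.1.5.4 and Protocol Appendix 8:

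- Keep the non-binding bound of 1 or fewer of 17.
- Say that Rho(2) and 0.117 describe an approximate derivation only, and name the method and variance once the sponsor has confirmed them from the design file.
- Replace the claim of Type 2 error control with exact figures: probability of meeting the bound 0.050 at ORR 25% and 0.482 at ORR 10%; total Type 2 error 0.179 if the rule is always followed and 0.155 with no look.

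If Rho(2) spending is meant to hold exactly, the bound consistent with it at 17 patients is 0 of 17, with stop probabilities 0.0075 at ORR 25% and 0.167 at ORR 10% and total Type 2 error 0.158. That option recovers about 2.1 points of power but gives up most of the early stopping of an inactive regimen.

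Keeping the bound costs wording in two places and no extra patients. The drawback is that the published Type 2 error becomes less favourable.
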